## **5.3 Treatment assignment and randomization**

At Visit 199, patients will be scheduled to undergo a PET scan. PET scan images will be centrally read by the imaging vendor to classify a patient as amyloid positive or amyloid negative. Patients will be stratified at Visit 201 according to their amyloid status within 3 to 5 days after acquisition of the baseline PET image. The investigator will remain blinded to the amyloid status. Since it may take several days to obtain results, it is recommended that the site take this into consideration when scheduling Visit 201, while keeping the patient on study medication. All eligible patients will be randomized via Interactive Response Technology (IRT) to one of the treatment arms. The investigator or his/her delegate will contact the IRT after confirming that the patient fulfills all the inclusion/exclusion criteria. The IRT will assign a randomization number to the patient, which will be used to link the patient to a treatment arm and will specify a unique medication number for the first package of investigational treatment to be dispensed to the patient. The randomization number will not be communicated to the caller.

The randomization numbers will be generated using the following procedure to ensure that treatment assignment is unbiased and concealed from patients and investigator staff. A patient randomization list will be produced by the IRT provider using a validated system that automates the random assignment of patient numbers to randomization numbers. These randomization numbers are linked to the different treatment arms, which in turn are linked to medication numbers. A separate medication list will be produced by or under the responsibility of Novartis Drug Supply Management using a validated system that automates the random assignment of medication numbers to packs containing the investigational drug(s).

Randomization will be stratified by three factors, age (<75, ≥75 years old), MMSE summary score at baseline (<28, ≥28), and brain amyloid status (unknown, amyloid (+) or amyloid (-)). Note that patients who do not participate in the PET imaging sub-study will be classified as having unknown amyloid status.

The randomization scheme for patients will be reviewed and approved by a member of the Novartis Randomization Group.

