#### 9.4.2 Statistical model, hypothesis, and method of analysis

The change from baseline in the GCCS of CogState test battery will be analyzed using a repeated measures analysis of covariance (ANCOVA) model in which treatment, age stratification factor, MMSE stratification factor, education level, APOE4 status (carrier vs. non-carrier), baseline cerebrovascular disease burden as measured by MRI (calculated based on four factors: lacunar infarcts > 2; cortical or subcortical infarct > 1cm^3; white matter lesion

Fazekas score of 3; micro hemorrhages  $\geq 4$ ), visit (Weeks 26, 52, 78, 104, 130 and Week 156) and treatment-by-visit interaction are included as fixed-effect factors and baseline GCCS and visit by baseline GCCS interaction as covariates, with a common unstructured covariance matrix among visits between treatment group. The adjusted mean changes at 3 years (Week 156) within each treatment, the difference in mean changes at 3 years (Week 156) between the two treatments, and its 95% confidence interval obtained from the above model will be presented. In addition, the treatment difference (LCZ696-valsartan) in mean changes from baseline to 3 years will also be expressed based on a standardized effect size (Cohen's d) with a 2-sided 95% confidence interval. The Cohen's d will be estimated by using the adjusted between-treatment mean difference, divided by the estimated standard deviation, which is calculated from the standard error of the adjusted mean change and the sample number of patients within each group (the pooled SD) from the above modeling. The analysis is based on likelihood method with an assumption of missing at random (MAR) for missing data.

As the primary analysis, this repeated measure ANCOVA model will be performed in the Safety set including 'on-treatment' data collected prior to the start of treatments for AD or cognitive impairment. The Cohen's d based on the adjusted difference in mean changes at 3 years (Week 156) between two treatments and its 95% confidence interval from this model will be used to draw the main conclusion for the primary objective. On-treatment data refer to cognitive test data collected while patients are on-study-medication (regardless of treatment interruption) or within three months after final study drug intake date.

In addition, the same repeated measure ANCOVA model will be performed in the following two analysis sets as supportive analyses:

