## 9.5 Analysis of secondary variables

### 9.5.1 Efficacy variables

The secondary variables are:

1. Change from baseline in individual cognitive domains (memory, executive function, and attention) as assessed by the individual components of the cognitive assessment battery at 3 years;
2. Change from baseline in the summary score of the instrumental activities of daily living (IADL) as assessed with Functional Activity Questionnaire (FAQ) at 3 years.

The composite z-scores by individual cognitive domains (memory, executive function, and attention) are defined in [Section 9.4.1](#).

For secondary variables composite z-scores by individual domain (memory, executive function and attention) and IADL, the changes from baseline to 3 years will be analyzed using the same repeated measures ANCOVA model as described in [Section 9.4.2](#) but with baseline GCCS replaced with respective secondary variable baselines. The adjusted mean changes at 3 years (Week 156) within each treatment, the difference in mean changes at 3 years (Week 156) between two treatments, its 95% confidence interval obtained from the above model will be presented. The analysis is based on likelihood method with an assumption of missing at random for missing data, and will be performed in the Safety set including ‘on-treatment’ data collected prior to the start of treatments for AD or cognitive impairment. On-treatment data are those collected while patients are on-study-medication (regardless of treatment interruption) or within three months after final study drug intake date. This analysis will be performed in the SAF.

In addition, as supportive analysis, similar repeated measure ANCOVA model will be also performed for these secondary endpoints for all data in the FAS.

Summaries of absolute values and change from baseline by treatment group and visit will be presented. Figures will be produced to visually show the endpoint values (SUVr, composite z-scores by cognitive domain and IADL) by visit over the study period for each treatment group. These analyses will be done in both SAF and FAS, for ‘on-treatment’ data and for all data, respectively.

For these secondary variables, a three month window will be applied to re-map any unscheduled visit assessments to a missing scheduled visit assessment.

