Captopril	100 mg	Candesartan	16 mg
Cilazapril	2.5 mg	Eprosartan	400 mg
Enalapril	10 mg	Irbesartan	150 mg
Fosinopril	20 mg	Losartan	50 mg
Imidapril	10 mg	Olmesartan	10 mg
Lisinopril	10 mg	Telmisartan	40 mg
Moxepril	7.5 mg	Valsartan	160 mg
Perindopril	4 mg		
Quinapril	20 mg		
Ramipril	5 mg		
Trandolapril	2 mg		
Zofenopril	30 mg		

Randomized treatment epoch

At the end of treatment run-in, patients who meet the protocol specified safety criteria as assessed by central or local laboratories and tolerate LCZ696 100 mg bid for at least 2 weeks are eligible for randomization. Patients will be randomized in a 1:1 fashion to either LCZ696 200 mg bid or valsartan 160 mg bid. The randomization will be stratified based on age (< 75, ≥ 75 years), MMSE score (< 28, ≥ 28), and baseline brain amyloid status (unknown, amyloid positive, amyloid negative).

With an expected screening and run-in failure rate of approximately 40%, it is estimated that approximately 870 patients will be screened at more than 150 centers worldwide to randomize approximately 520 patients. A subset of about 430 randomized patients will be enrolled in the amyloid PET imaging substudy.

There is no formal interim analysis planned for efficacy. Interim safety data will be reviewed by an external Data Monitoring Committee (DMC) regularly as specified in the DMC charter. The final analysis is planned to be executed at the completion of all planned assessments for last randomized patient.

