2.5.2 Statistical hypothesis, model, and method of analysis

The change from baseline in the GCCS of CogState test battery will be analyzed using a repeated measures analysis of covariance (ANCOVA) model in which treatment, age stratification factor, MMSE stratification factor, education level, APOE4 status (carrier vs. non-carrier), baseline cerebrovascular disease burden, visit (Weeks 26, 52, 78, 104, 130 and Week 156) and treatment-by-visit interaction are included as fixed-effect factors and baseline GCCS and visit-by-baseline GCCS interaction as covariates, with a common unstructured covariance matrix among visits between treatment groups. The adjusted mean changes at 3 years (Week 156) within each treatment, the difference in mean changes at 3 years (Week 156) between the two treatments, and its 95% confidence interval obtained from the above model will be presented. In addition, the treatment difference (LCZ696-valsartan) in mean changes from baseline to 3 years will also be expressed based on a standardized effect size (Cohen's d) with a 2-sided 95% confidence interval. The Cohen's d will be estimated by using the adjusted between-treatment mean difference, divided by the estimated pooled standard deviation. The estimated standard deviation for the mean difference is:

$$SD = \left(\frac{1}{n_1} + \frac{1}{n_2} \right)^{1/2} \hat{\sigma}$$

where n1 and n2 are the number of patients within each treatment group and $\hat{\sigma}$ is the pooled standard deviation of the within treatment group adjusted mean change. Cohen's d can be rewritten in terms of t value of the estimated between treatment group difference based on the adjusted mean changes from the model mentioned above:

$$t = \frac{\hat{\mu}_1 - \hat{\mu}_2}{SD} = \frac{\hat{\mu}_1 - \hat{\mu}_2}{\left(\frac{1}{n_1} + \frac{1}{n_2} \right)^{1/2} \hat{\sigma}}$$

$$\hat{d} = \frac{\hat{\mu}_1 - \hat{\mu}_2}{\hat{\sigma}} = \left(\frac{1}{n_1} + \frac{1}{n_2} \right)^{1/2} \times t$$

Confidence interval (CI) of Cohen's d is based on 95% CI of the noncentrality parameter of t value divided by the square root of the degrees of freedom from the estimated between treatment group adjusted mean change (Cumming and Finch 2001). The analysis is based on a direct likelihood method with an assumption of missing at random (MAR) for the missing data mechanism.

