1. Multiple (e.g. 100) imputations of missing GCCS values under a MAR assumption are generated, resulting in multiple (100) complete data sets. This imputation is based on predicted GCCS values from the fitted repeated measures ANCOVA model for the GCCS values (at baseline, Weeks 26, 52, 78, 104, 130 and Week 156) with treatment, age group (<75, ≥75 years), baseline MMSE status (<28, ≥28), baseline cerebrovascular disease burden, visit and treatment-by-visit interaction as factors having fixed effects assuming a common unstructured covariance matrix among visits between treatment group. SAS proc MI FCS statement is used to impute missing values in the following sequence: factor variables in the increasing order of missing frequency, the GCCS at baseline, Weeks 26, 52, 78, 104, 130 and Week 156.
2. For each completed data set, the imputed GCCS values at a given visit for patients who died, or had a HF hospitalization or stroke since the preceding visit, a penalty factor would be applied to the imputed values to reflect that the MAR approach may have overestimated the missing values, e.g. by assuming the actual GCCS values could be a certain percentage (e.g. 5%) worse than MAR based imputations for discontinuations due to death, HF hospitalization and stroke. If the MAR-imputed GCCS value is positive, the final value will be 95% x the imputed value; if the MAR-imputed GCCS value is negative, the final value will be 105% x the imputed value.
3. The primary analysis model as described above will be fitted to the 100 completed data sets following the application of the penalty factor in step 2 which produces 100 sets of parameter estimates and associated covariance matrices.
4. These 100 sets of parameter estimates are then combined by using Rubin's rules to derive overall estimates and their confidence intervals. In a similar manner to the primary analysis, a standardized effect size estimate (Cohen's d) and 95% CI will also be reported using the pooled SD.

The analysis will be repeated for varying penalty factors in a range between 0 and 50%. It is performed using 'on-treatment' data in the SAF, as done in the primary analysis. Tipping point analyses will be performed separately to assess the sensitivity of the results to MAR assumptions under the following situations:

- for missing data due to censoring at the start of AD and cognitive impairment treatments, including on-treatment data only in the SAF

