- for missing data due to withdrawal for unknown reasons, including on-treatment data only in the SAF
- for missing data due to censoring at the start of AD and cognitive impairment treatments, including all data in the FAS
- for missing data due to withdrawal for unknown reasons, including all data in the FAS

In a similar procedure, missing values due to respective reasons will be imputed assuming MNAR while assuming all other missingness mechanism to be MAR.

If model convergence issue arises in the tipping point analysis, the model in step 1 above will be modified by replacing the common unstructured covariance matrix with a compound symmetry covariance matrix between treatment groups. If convergence issue remains after implementing the compound symmetry covariance matrix, the model will be simplified by removing baseline cerebrovascular disease burden as explanatory factor from the model.

Joint model approach

To adjust for the non-ignorable missingness in the primary endpoint due to starting AD/CI related medication, a joint modeling of the primary longitudinal process and missingness mechanism will be performed using a shared parameter approach (Vonesh et al 2006). Specifically, a generalized linear mixed model (GLMM) for the longitudinal GCCS outcome and a Cox proportional hazard model for the time to starting AD/CI related medication will be fitted which share common unobserved patient-specific random effect. It is assumed that the longitudinal outcome process is independent of the time to starting AD/CI related medication conditional on the random effects.

Model for longitudinal outcomes

The repeated GCCS outcomes will be analyzed following a repeated measures ANCOVA model with treatment, age stratification factor, MMSE stratification factor, education level, baseline cerebrovascular disease burden, APOE4 status (carrier vs. non-carrier) are included as factors and baseline GCCS, assessment time (in days), assessment time by baseline GCCS and assessment time by treatment interaction as covariates having fixed effects. Further, a patient-specific random intercept and random slope (on time) is fitted to the model. In general, the model has the following mathematical form:

$$y_i(t) = m_i(t) + e_i(t)$$
$$m_i(t) = X_i^T(t)\beta + (b_{0i} + b_{1i}t)$$

where

$y_i(t)$ =GCCS outcome for i-th patient at time t (assessment time in months)

$m_i(t)$ = 'True' (unobserved) patient-specific mean GCCS outcome for i-th patient at time t

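### Brain amyloid status is one of three randomisation strata but is left out of the GCCS, domain and FAQ models without a stated reason (minor; no bias, and a gain probably close to nil)

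*SAP*

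**What the plan says.** Protocol 5.3 states: "Randomization will be stratified by three factors, age (<75, ≥75 years old), MMSE summary score at baseline (<28, ≥28), and brain amyloid status". The third factor has a value for everyone randomised, because "patients who do not participate in the PET imaging sub-study will be classified as having unknown amyloid status". SAP 1.1 gives the same three levels: "baseline brain amyloid status (unknown, amyloid positive, amyloid negative".

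The GCCS model in Protocol 9.4.2 lists "treatment, age stratification factor, MMSE stratification factor, education level, APOE4 status" and goes on to cerebrovascular burden, visit and baseline GCCS. SAP 2.5.2 has the same terms: "treatment, age stratification factor, MMSE stratification factor, education level, APOE4 status (carrier vs. non-carrier), baseline cerebrovascular disease burden, visit". Age and MMSE enter as stratification factors; amyloid does not enter.

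The same gap recurs elsewhere:

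- **Domain scores and FAQ.** Protocol 9.5.1 says that these "will be analyzed using the same repeated measures ANCOVA model as described in" section 9.4.2, with only the baseline replaced. SAP 2.6.2 does likewise with 2.5.2.
- **Tipping-point imputation model (SAP 2.5.5).** Its terms are "treatment, age group (<75, ≥75 years), baseline MMSE status (<28, ≥28), baseline cerebrovascular disease burden, visit and treatment-by-visit interaction as factors".
- **Joint model (SAP 2.5.5).** For the longitudinal part, "treatment, age stratification factor, MMSE stratification factor, education level, baseline cerebrovascular disease burden, APOE4 status (carrier vs. non-carrier) are included as factors".

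Amyloid status does appear in two other places. It is an efficacy subgroup in SAP Table 2-1, and SAP 2.5.4 adds the subgroup and its interaction with treatment to obtain the interaction p-value. The SUVr models in SAP 2.7.1 and 2.7.1.1 carry it as a positive/negative factor.

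**The concern.** Stratified allocation makes the arms alike on the stratum. A model that leaves the stratum out still counts the between-stratum variance as residual error, so its standard error is too large for the design actually used. The usual practice is to analyse by the factors used to randomise, or to explain why not. Here two of three are in the model and the third is dropped without comment.

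The protocol gives grounds to think that amyloid is prognostic: section 3.2 says that cognitively normal older adults with raised amyloid progress faster over 36 months. What is at stake is a little precision on the raw difference, slightly conservative error rates, and agreement between the analysis and the randomisation.

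**Working it through.** **The plan's own sizing.** With d = 0.3 and two-sided 5%, n per arm = 2(1.960 + 0.842)²/0.3² = 174.5, so 175, against 180 stated. At 180 per arm the noncentrality is 0.3/√(2/180) = 2.846 and t-based power is 81.0%. For 30% loss, 360/0.7 = 514.3, so 515, against 520 stated. The sizing holds and does not depend on the amyloid term.

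**Inputs that the documents do not give (assumed).** These are the number of amyloid-positive patients, the GCCS gap between positives and the rest, the share of residual variance that amyloid explains beyond the terms already fitted (R²), and the block size. For positives I take 2%, 5% or 10% of the 430 PET patients, which is 9, 22 or 43. The gap is 0.3 or 0.5 residual SD. Patients of unknown status are given the same mean as negatives. With p = positives/520, R² = p(1 − p) × gap²:

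| Positives | Gap 0.3 SD | Gap 0.5 SD |
|---|---|---|
| 9 | 0.15% | 0.43% |
| 22 | 0.36% | 1.01% |
| 43 | 0.68% | 1.90% |

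So R² of about 0.15% to 2% covers the range.

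**Effect of the omission with exact balance within strata.** This is a single-time-point approximation at Week 156 with 180 per arm, total residual SD 1 and k = √(1 − R²). The true SE of the difference is k√(2/180), but the model without amyloid reports √(2/180). Its interval is therefore too wide by 1/k − 1, its actual two-sided alpha is 2P(t₃₅₈ > 1.967/k), and power follows from the noncentral t (358 df without the term, 356 with it).

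| R² | Raw CI too wide by | Actual alpha | Power at 0.3, term out | Term in | Loss (points) |
|---|---|---|---|---|---|
| 0.15% | 0.08% | 4.98% | 81.03% | 81.07% | 0.04 |
| 0.4% | 0.20% | 4.95% | 81.06% | 81.17% | 0.11 |
| 1% | 0.50% | 4.89% | 81.13% | 81.40% | 0.27 |
| 2% | 1.02% | 4.77% | 81.25% | 81.79% | 0.53 |

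**Allowing for imperfect balance.** Exact balance flatters the term. A simulation assumed permuted blocks of 4 in 12 strata (90 patients of unknown status) and random loss from 520 to 360, over 12,000 allocations, and charged the model for two extra terms (variance inflation 1.0020 to 1.0026). The change in power from adding the stratum, in points (simulation SE 0.02 or less), was:

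| Positives | Gap 0.3 SD | Gap 0.5 SD |
|---|---|---|
| 9 | −0.06 | +0.03 |
| 22 | +0.05 | +0.27 |
| 43 | +0.14 | +0.51 |

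**Cohen's d interval at d = 0.** The noncentrality limits are ±1.960. Multiplied by √(1/180 + 1/180), the half-width is 0.207 with or without the term, because d is scaled by the model's own SD. Divided by the square root of the degrees of freedom, as SAP 2.5.2 is worded, it is 1.960/√358 = 0.1036 without the term and 1.960/√356 = 0.1039 with it. Neither scaling gives a narrower interval.

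**What d = 0.3 then means.** With the term in, d = 0.3 corresponds to 0.3k on the present scale: 0.2998 at R² = 0.15% and 0.2970 at R² = 2%, a shift of at most about 1%.

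**The case against.** The best case for leaving the model alone has four parts.

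1. **The gain is not shown to be real.** This largely stands. The SAP document history for June 2022 reports very few amyloid-positive patients, and APOE4, which Protocol 3.1 calls a strong predictor, is already in the model. Both point to the low end, where the change in power is about zero and can be slightly negative.
2. **Sparsity was a known problem.** The same history entry cites a convergence difficulty as well as the small number of positives. That arose when SUVr was imputed separately within the positive stratum, and the remedy was to enter amyloid as a factor. It does not show that a fixed factor would fail in the GCCS model, but it does justify a rule for dropping the term.
3. **The SUVr models are not a template.** This stands. They use two levels within the PET substudy. In the main trial the unknown level, about 90 of 520 patients, marks non-participation in PET, which under Protocol 3.1 depends largely on the centre. It is a randomisation category, not a biological one.
4. **Amyloid is already examined as a subgroup, and Protocol and SAP agree on the model.** Both are true. A subgroup interaction test is not an adjusted primary estimate, and agreement between the two documents is not a reason for the omission.

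A reader might infer that the omission biases the treatment effect, inflates type I error or leaves the trial underpowered. The documents support none of these: allocation is randomised 1:1, the calculated error is on the conservative side, and the sizing reproduces. Nor can it be said that amyloid is absent from every cognitive analysis, because redacted exploratory analyses cannot be checked.

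**Conclusion.** The point holds as a minor one. The GCCS, domain and FAQ models adjust for two of the three randomisation strata, and the visible text does not say why. The raw-difference interval and the test against zero are at most slightly conservative: 0.08% to 1.02% in width, and an actual alpha of 4.98% to 4.77%, for assumed R² of 0.15% to 2% under exact balance. The Cohen's d interval, on which SAP 2.5.2 rests the main conclusion, does not narrow. With few positives the net effect on power is probably close to nil.

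These sizes rest on assumed R², number of positives, gap and block size; the direction does not. The case for the change is that the analysis would follow the randomisation. It is not a case for better precision.

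**What to change.** Before unblinding:

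- Add the three-level amyloid stratum, as held in the randomisation system, as a fixed-effect factor in SAP 2.5.2. SAP 2.6.2 and the mis-stratification re-run in 2.5.5.1 then inherit it. Describe it as the randomisation factor, not as a copy of the two-level SUVr factor.
- State that if the model does not converge, amyloid is dropped first and the existing order in 2.5.2 then applies. The term then cannot trigger the switch to compound symmetry.
- Record the change in SAP section 4, which now reads as not applicable, as a departure from Protocol 9.4.2.
- Optionally, add the stratum to the tipping-point imputation model and the longitudinal part of the joint model in 2.5.5. Each has its own convergence provisions, so the same drop-first rule must be written into both. The imputation model already lacks education and APOE4, so adding amyloid alone would not align it with 2.5.2.
- If the present model is kept, one sentence of reason in 2.5.2 closes the point.

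The cost is up to 2 degrees of freedom, about 0.2% to 0.3% variance inflation, a sparse positive level, the very small shift in what d = 0.3 means on the raw scale, and a short documentation edit. No new data are needed.
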